8. RATIONALE

Despite recent achievements in reducing child mortality, neonatal deaths remain high, accounting for 46% of all deaths in children under 5 worldwide. Neonatal mortality in Kenya is reported to be 22.6 per 1000 live births, ranking among the countries with the highest number of neonatal deaths. Addressing the high neonatal mortality demands efforts focused on getting proven interventions to at-risk neonates and their families. Bidirectional two-way SMS communication with a HCW presents a unique opportunity to connect mothers to a HCW, increase "real-time" identification of neonatal danger signs and guide appropriate care seeking. At the same time, this communication can provide support to women during the critical peripartum period, increase self-efficacy and social support, and contribute to decreasing depressive symptoms, which may further improve care seeking. SMS communication is designed to supplement, not to replace, in person health care delivery. We propose a randomized controlled trial (RCT) of a semi-automated, two-way SMS intervention, **Mobile WACh NEO**, to determine its effect on neonatal mortality, implementation of ENC, identification of and appropriate care seeking for neonatal illness, and maternal mental health.

9. HYPOTHESIS & STUDY QUESTIONS:

Our overarching hypothesis is that Mobile WACh NEO, a theoretically grounded two-way SMS intervention that connects women with healthcare workers in the critical period surrounding delivery of their babies, will improve their knowledge, skills and motivation to prevent, identify and seek care for neonatal illness, leading to improved maternal and neonatal health.

10. OBJECTIVES

10.1 Broad Objectives

Our overarching aim is to determine the effect of Mobile WACh NEO SMS on neonatal mortality and understand the mechanisms by which this innovation impacts neonatal health. **We propose to determine the effect of Mobile WACh NEO SMS on neonatal mortality, essential newborn care, care seeking, and maternal mental health in the first 6 weeks postpartum, in a 2-armed randomized controlled trial (RCT), comparing essential newborn care SMS versus no SMS control.**

10.2 Specific Objectives

Aim 1: To determine the effect of tailored, systematic two-way Mobile WACh NEO SMS on neonatal mortality.

Hypothesis: Women randomized to Mobile WACh NEO will have lower neonatal mortality than women randomized to control.

Aim 2: To determine the effect of Mobile WACh NEO SMS on maternal implementation of essential newborn care and care seeking behavior.

2a. To compare practices of early and exclusive breastfeeding, cord care and thermal care among mothers randomized to Mobile WACh NEO versus control.

2b. To compare knowledge of infant danger signs and care seeking for neonatal illness among mothers randomized to Mobile WACh NEOv uersus control.

Hypothesis: Implementation of essential newborn care, knowledge of neonatal danger signs, and clinic attendance will be higher in mothers randomized to Mobile WACh NEO SMS than control.

Aim 3: To determine the effect of Mobile WACh NEOSMS on longitudinal maternal social support, self-efficacy and depression among mothers randomized to Mobile WACh NEOversus control.

Hypothesis: Maternal self-efficacy and social support will be higher and depression will be lower among women randomized to Mobile WACh NEO than control.

Exploratory aim: To determine associations between maternal mental health, implementation of essential newborn care, care seeking and SMS engagement.

11. METHODOLOGY

11.1 Study Design

The study is a non-blinded randomized controlled trial.

11.2 Study Area Description

Study sites: The proposed study will be conducted at 11 sites in Kenya: Mathare North City Health Centre, Riruta Health Centre, Rachuonyo South County Hospital, Ahero sub-District Hospital, Bondo District Hospital, Kisumu County Hospital, Migosi Sub-County Hospital, Lumumba Sub-County Hospital, Homa Bay County Referral Hospital, Rangwe Sub County Hospital and Rachuonyo North Sub County Hospital. Neonatal mortality in the Nairobi slum areas, Kisumu and Homa Bay counties is particularly high (4) so communities in these areas stand to benefit the most from the Mobile WACh NEO intervention. These facilities represent a mix of rural and urban facilities, all with sufficient patient volume to assure feasibility of recruitment. From our ongoing studies at these sites we estimate ~260 women attend ANC per month at each site.

Letters of cooperation will be submitted in a subsequent modification to this application.

11.3 Study Population

Table 2. Summary of proposed eligibility, procedures and outcomes for study aims

Population	N	Inclusion Criteria	Data Collection
------------	---	--------------------	-----------------

RCT			
Pregnant women	5020	
 • Pregnant • 28-36 weeks gestation • Daily access to a mobile phone (own or shared) on the Safaricom network • Willing to receive SMS • Age ≥ 14 years • Able to read and respond to text messages in English, Kiswahili or Luo, or have someone in the household who can help • 	
 • Screening questionnaire • Enrolment and follow-up questionnaires • Content of SMS conversations with Mobile WACH system
Post-RCT IDIs			
Postpartum women	60	Intervention RCT participant	
 • IDI

Study populations for each of the aims are summarized in Table 2. Two study populations will be included in the study:

1. Pregnant women (Randomized controlled trial) (N=5020)

Inclusion criteria:

- Age ≥ 14
- Pregnant
- 28-36 weeks gestation
- Daily access to a mobile phone on the Safaricom network
- Able to read and respond to text messages in English, Kiswahili or Luo, or have someone in the household who can help

Exclusion criteria:

- Currently enrolled in another research study
- Previous participant in the Mobile WACH NEO RCT (i.e. with a new pregnancy)

To enhance generalizability, literacy will not be required if women have access to a partner or family member whom she would be comfortable to have read her the messages. This approach was developed in consultation with mothers in Kenya, who felt that involving their partner was acceptable and may engage more support, and has been successfully implemented in our previous Mobile WACH studies.

2. Postpartum women (post-RCT IDIs) (N=60)

A subset of intervention RCT participants will be invited to participate in IDIs after they complete the intervention to evaluate their experiences with the intervention.

11.4 Sample Size Determination

11.4.i. RCT

Table 4 summarizes detectable differences based on the expected outcomes, assuming $\alpha=0.0055$ (Bonferroni-adjusted for 9 hypothesis tests) and sample size 5020 (2510 per arm). Expected outcomes are based on those observed in our previous work in Kenyan pregnant women (unpublished data) (58, 64) or other publications (68).

Table 3. Power and sample size ranges.

Indicator	Minimum detectable difference			
	Outcomes (control)	Outcomes (intervention)	Absolute difference	Relative difference
Neonatal mortality per 1000 births ¹	25.0	13.8	11.2	0.55
	23.0	12.2	10.8	0.53
	20.0	10.0	10.0	0.50
Initiation of BF within 1h; EBF for 6 weeks ²	90.0%	93.0%	3.0%	1.03
	80.0%	84.1%	4.1%	1.05
Application of substances to cord; Bath within 24h ²	40.0%	45.3%	5.3%	1.13
	50.0%	55.4%	5.4%	1.11
Number of clinic visits in first 6 weeks ²	0.5	0.6	0.1	1.22
	1.0	1.1	0.1	1.11
Number of danger signs correctly named ²	3.0	3.1	0.1	1.03
	5.0	5.1	0.1	1.02
Maternal depression ²	19.0%	14.6%	4.4%	0.77
Maternal social support score; Maternal self-efficacy score (max 4.0) ²	2.5	2.6	0.1	1.04
	3.5	3.6	0.1	1.03

¹ $\alpha=0.05$, ²Adjusted $\alpha=0.0055$, $\beta=0.8$, 2-sided tests

11.4.ii. IDIs

Sample size for qualitative data collection was determined based on the number of interviews needed to achieve saturation of concepts. It is estimated that 60 interviews will be sufficient to achieve saturation.

11.5 Recruitment, Screening and Consent Procedures

11.5.i. RCT

Recruitment: Women will be recruited when attending routine ANC, through in-person outreach by study staff.

Screening and consent: Interested patients will be asked to provide verbal consent for screening (see screening consent script), consenting women will be asked screening questions to assess eligibility and, if eligible (see inclusion criteria above), be invited to participate in the study. Women willing to participate in the study will be asked to provide written informed consent form. The age of consent in Kenya is 18, but pregnant women age 14 or older are considered emancipated minors and can consent independently. Discussions between study staff and potential participants will be conducted in a private secluded place to maintain privacy.

11.5.ii. IDIs

Recruitment: Participants from the intervention arm will be classified into high, medium and low interactors based on their engagement or use of the Mobile WACh NEO program i.e. how often they send or respond to SMS. We will then randomly select 10 from each group to participate in interviews (IDIs). They will be invited to participate in IDIs while they are still on-study. We will also interview 30 women among those with neonatal complications or demises. Based on our previous studies we anticipate that half of the women who lose their babies want to remain connected to the program. We

will select women for IDIs from among those who agree to remain connected to the program even after their loss.

11.6 Data Collection Procedures

11.6.i. RCT

Intervention package: We propose to utilize Mobile WACH, a human-computer hybrid system used in our previous studies, which enables seamless two-way SMS communication and patient tracking, to provide consistent support to women and their infants during the peripartum period and 6 weeks into the baby's life. Women will receive automated theoretically grounded SMS messages targeting the appropriate peripartum period (Figure 10) and will have the capability to respond and spontaneously message a nurse based at the clinic. During pregnancy, automated SMS will be delivered weekly.

Two weeks prior to the participant's estimated due date (EDD), daily messaging will begin, and will continue for two weeks after delivery is ascertained. If delivery is not confirmed by 43 weeks gestational age, the participant will be automatically moved to the postpartum messaging track. Thereafter, SMS will be delivered every other day for the remaining four weeks. Automated SMS will be delivered at times and in languages based on patient preferences. We have partnered with a local premium rate service provider (PRSP), Africa's Talking, to provide SMS dialogue free of charge to participants. Women who experience pregnancy or infant loss will be enrolled into an infant loss track where they will receive messages of support.

[figure not shown]
[figure not shown]

Figure 10. Mobile WACH NEO intervention. Women who experience pregnancy or infant loss will be enrolled into an infant loss track where they will receive messages of support.

Randomization:

Participants will be randomized to 1) Interactive two-way SMS dialogue or 2) Control (no SMS), using 1:1 allocation. A randomization list will be generated by the study statistician using random block sizes in statistical software. Randomization will be stratified by site. This randomization list will be programmed into a computer program on an internet-based randomization platform. Each study site will be assigned unique user names and log in credentials for traceability purposes and ensuring that the randomization process is controlled. Study staff will use their unique credentials to log in to the randomization program. The program will display

the allocation after staff have entered the participant ID. The allocation will be recorded in the program for further traceability. The study arm will be unblinded to participants and study staff. The control arm will receive standard care and education provided in ANC by MCH clinic staff. Because the study aims to determine mHealth benefits in addition to routine clinical care, MNCH services will be delivered by the MOH programs with minimal clinic interactions with study personnel. The intervention will be delivered between 28 weeks of gestation and 6 weeks postpartum.

Data collection:

Participants will be followed from enrolment (28-36 weeks gestation) up to 18 weeks postpartum. All clinical care will be managed through the existing MCH infrastructure. The study visit schedule will be aligned to routine postpartum and infant visits: enrolment visit in pregnancy (28-36 weeks gestation), 2 weeks postpartum and 6 weeks postpartum. Active tracing will be performed through phone calls and home visits to maximize completeness of data at study visits. Participants who do not report their delivery by 40 weeks will be contacted by phone, followed by home tracing if not reached by phone. Further, participants who are 1 week late for their 2-week or 6-week postpartum visits will be traced by phone. Participants who are 1 week late for their 6-week visit and cannot be reached by phone will be traced at their home. Participants who do not wish to come to clinic for their 2-week or 6-week visit will be offered to complete their visits **by phone or at home** in locations that ensure participant safety.

and confidentiality. This approach has been successful and acceptable in our previous studies in this population (31, 64, 69). During the consent process, study staff will collect contact information and permission to contact a family member or trusted individual who they may contact in case of long-term lack of communication from the participant. This person may be contacted as part of active tracing. In the case of a maternal death or disappearance, staff will collect information on the event from the provided contact.

A tablet-based screening questionnaire will be used to assess eligibility and collect sociodemographic characteristics. Following enrolment in the RCT and randomization, a tablet-based enrolment questionnaire using an open-source tablet-based data collection system (Open Data Kit) will be used to collect enrolment data including: demographics, clinical and sexual history, family planning, experience with SMS and technology, social support, intimate partner violence, and depression.

At each visit, a standardized questionnaire will evaluate self-reported outcomes (Table 4), experience with the intervention (for intervention participants) and participant clinical characteristics that may be associated with the outcomes, such as delivery experience, maternal and child health status, breastfeeding, care-seeking, cord care, depression and social support. Between study visits, data will be abstracted from patient clinic records to ascertain clinical outcomes such as deliveries, clinic/hospital visits, and infant or maternal deaths (Table 4). The data will be abstracted from available facility records including MCH cards, facility registers (hospitalization, ANC, CWC, PNC), and EMR systems. The study nurses will review clinic records daily to check for deliveries and clinic visits from study participants. We have successfully employed this approach in a previous RCT, Mobile WACH-X (64). In addition to contributing to ascertainment of trial outcomes, abstraction of clinic records will enable personalization of messaging, for example initiating postpartum messaging after a participant delivers.

Medical extraction forms will be completed by data teams: delivery information, infant admissions, maternal health, infant health, maternal mortality, and infant mortality.

When the study team learns of an infant death through an SMS message, phone call or clinic record review, the study team will contact the participant to arrange a visit to conduct a verbal autopsy. Verbal autopsies will be performed about 6 weeks after the infant death, either in the clinic or at the participant's home based on their preference.

Participants will be provided Ksh. 400 per visit to compensate for time and transportation expenses to participate in the study. We will provide this monetary compensation to each participant at the conclusion of each study visit. In the case of a maternal death or disappearance, the contact from whom the information on the event was collected will be provided Ksh. 400 to compensate for time.

Data collection instruments

Data collection instruments will include forms to record data from participant surveys, to include:

- Demographics
- Clinical and sexual history
- FP use
- Experience with SMS and technology
- Intimate partner violence
- Depression
- Social support
- Delivery report
- Infant health
- Maternal health

11.6.ii. IDIs

IDIs will be performed in a private area within the facility. Participants will meet a trained interviewer who will ask questions and take notes. Consent will be obtained from participants to take notes and audio record the discussion. The interviewer will describe procedures and norms for discussion and participation. Participants will be given a chance to ask questions regarding procedures prior to the discussion. Their socio-demographic information will be documented in separate forms. Socio-demographic information that will be captured include: age, marital status, education level, employment, number of children.

We will submit an IDI guide in a future modification.

Interviews will be conducted in English, Kiswahili, or Luo depending on participant preferences. Thereafter, notes will be compared to audio-recordings to fill in missing information and transcribed to English (if necessary). Transcribed data will be de-identified. Tape-recorded discussions will be destroyed no later than 3 years after conducting the IDI.

Participants will be provided refreshments and Ksh. 400 to compensate for time and transportation expenses to participate in the study. We will provide this monetary compensation to each participant at the conclusion of each interview.

11.7 Data Analysis

Table 4: RCT outcomes

Outcome	Role	Indicator	Source	Timing of ascertainment	Statistical Analysis
Aim 1					
Neonatal mortality	Primary outcome	Death during 1 st 28 days of life	Questionnaire, clinic records; verbal autopsy	2 and 6 week visits, ongoing record abstraction	Cox proportional hazards
Aim 2					
Initiation of early breastfeeding	Secondary outcome	Breastfeeding in 1 st hour of life	Questionnaire	2 week visit	Poisson regression (robust standard errors)
Exclusive breastfeeding	Secondary outcome	Cessation of EBF in 1 st 6 weeks of life	Questionnaire	2 and 6 week visits	Cox proportional hazards
Thermal care	Secondary outcome	Bath in 1 st 24 hours of life	Questionnaire	2 week visit	Poisson regression (robust standard errors)
Cord care	Secondary outcome	No application of substances to cord	Questionnaire	2 week visit	Poisson regression (robust standard errors)
Maternal knowledge of neonatal danger signs	Secondary outcome	Number of the 7 danger signs or symptoms successfully named	Questionnaire	2 and 6 week visits	Poisson GEE
Appropriate care seeking	Secondary outcome	Number of clinic visits with danger sign and/or hospital admissions reported in 1 st 6 weeks	Questionnaire, clinic records	2 and 6 week visits, ongoing record abstraction	Poisson regression
Aim 3					

Depression	Secondary outcome	Score above diagnostic threshold (≥ 12) for Edinburgh Postnatal Depression Scale (70)	Questionnaire	Enrolment, 2 and 6 week visits	Poisson regression (robust standard errors)
Social support	Secondary outcome	Score using MOS Social Support Survey (71)	Questionnaire	Enrolment, 2 and 6 week visits	Linear GEE
Self-efficacy	Secondary outcome	Score using Self-efficacy in Infant Care Scale (68)	Questionnaire	Enrolment, 2 and 6 week visits	Linear GEE

For IDI analysis, two analysts will independently code transcripts to identify themes and sub-themes, coordinating analyses to create a comprehensive codebook and concept map. We will use domains identified under the IMB theory and our conceptual model to categorize participants' perceived intervention functions.

11.8 Study Materials

Equipment: The grant award includes support for SMS platform messaging delivery and receipt, 6 tablets, field office supplies (stationary, paper, toner), 6 laptop computers.

Personnel: The grant award includes support for KNH, UW and MOH investigators, clinic personnel, the data team, and two study coordinators (clinical coordinator (Nairobi based) and overall coordination (Seattle based)). Study personnel working in Kenya will be hired through KNH according to standard procedures.

11.9 Training Procedures

[name], [name], [name], [name], [name], [name], [name] and [name] will supervise training of clinical personnel in study procedures. This will include research ethics, neonatal health and FP counseling and completion of surveys.

11.10 Quality Assurance Procedures

Clinical care: The study will adhere to Government of Kenya guidelines for the care of pregnant/postpartum women and their infants; however, no clinical care will be provided by study staff. Data collected as part of the study will be abstracted from the mother's "Mother & Child Health Booklet" or clinic medical records.

Adherence to protocol: Weekly reporting of enrolment, follow-up, medical complications and results will enable us to monitor that the study is running according to approved protocols. Frequent reporting will also enable us to quickly respond to any problems that arise during the study.

12. ETHICAL CONSIDERATIONS

12.1 Consent explanation

Please see the attached consent forms:
Consent 1: RCT study participation

12.2 Institutional Review Board

This is a collaborative research proposal that will involve field procedures in Nairobi and data analyses in Nairobi and Seattle. The study will be reviewed by the Kenyatta National Hospital/University of Nairobi (KNH/UON) Ethics and Research Committee (ERC), and the University of Washington Institutional Review Board (IRB). The study will not recruit subjects prior to approval from both the UW IRB and the KNH/UON ERC.

12.3 Risks to subjects

Physical: The study involves no medical interventions therefore we anticipate no risk of serious harm to participants.

Other: SMS: There is a potential risk of disclosure of an individual's person information to others in situations where phones are shared or stolen. We will minimize these risks through counseling in the informed consent process and ensuring women understand the type of messaging that will occur.

Access to clinical records: There could be a breach of confidentiality in the process of retrieving participants' medical records. This will be mitigated by training all study staff on data management and storage to ensure confidentiality of sensitive data is maintained.

Loss of Confidentiality in IDI: Women will be notified that by participating in the IDI, loss of confidentiality is a possible risk of participating. They will be informed that this is very unlikely as every measure will be taken to ensure confidentiality.

Alternative treatments or procedures: Not applicable

12.4 Protection against risks

Informed consent: Study staff will give potential participants verbal and written information about the study. Consent will be obtained and documented in verbal and written forms. Participants will have a chance to ask questions about the study, and offered participation. They will be enrolled in the study after providing written informed consent. Mothers will provide informed consent for study participation on behalf of their infants.

SMS: There is a potential risk of disclosure of an individual's person information to others in situations where phones are shared or stolen. However, we will not send any sensitive information via text. Study staff will specifically demonstrate example messages, to ensure potential cohort study participants agree to receipt of this information. Participants will only be enrolled once they understand study procedures and find the messaging acceptable.

Access to clinical records: There could be a breach of confidentiality in the process of retrieving participants' medical records. This will be mitigated by training all study staff on data management and storage to ensure confidentiality of sensitive data is maintained. Databases will not include patient identifiers and will be encrypted and password protected.

Loss of confidentiality in IDI: We will assure women of protection of confidentiality.

DSMB: Clinical care will continue to be provided as prescribed. As this is a clinical trial, we will have a DSMB who will regularly monitor protocols and outcomes.

Undiagnosed conditions: It is possible we will detect previously undiagnosed conditions such as depression and intimate partner violence. Participants will be referred for appropriate health and social services.

SMS withdrawal: Participants in the intervention group may withdraw from receiving SMS messages at any time. Study staff will complete an SMS Withdrawal form for any participants who wish to withdraw from the system. Participants who withdraw from SMS can continue or withdraw from the study.

Study withdrawal: Participants may withdraw from the study at any time for any reason. The Study or Site PI may also terminate a participant from the study at their discretion, if she was enrolled inappropriately, or if continued participation would be harmful. Study staff will complete a Study Termination form for any participants choosing to terminate early. All data collection and SMS messaging will discontinue at that point.

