[name], Kenya 2015 (59, 60, 64)	Mobile WACh X	875 HIV infected peripartum women and infants	1-way SMS versus 2-way dialogue	RCT	Retention ART Adherence Viral suppression Drug resistance Infant HIV	Ongoing
[name], Kenya 2016 (58)	Mobile WACh XY	260 postpartum women and male partners	2-way SMS	RCT	Highly effective contraceptive (HEC) use	Improved HEC use postpartum
[name], Kenya 2017	Vijana - SMART	110 HIV-infected adolescents	WhatsApp peer group intervention	Pilot	Retention ART adherence	Ongoing
[name], US 2016 (66)	DAWN	25 women with perinatal depression in collaborative care	2-way SMS	Pilot	Process outcomes	Use of SMS for depression support acceptable and feasible
[name], Kenya 2016	Mobile WACh NEO	800 peripartum women and their infants	2-way SMS	Demonstration project	Process outcomes Facility delivery Contraception Neonatal mortality	Ongoing
[name], Kenya 2017	Mobile WACh PrIYA	300 young women and adolescent girls	2-way SMS	Demonstration project	Process outcomes PrEP adherence	Ongoing

[name], Kenya 2017	mCube	1,000 adolescents and adult women	Smart 2-way SMS for data collection	logic SMS data	Pilot	Process outcomes Contracepti ve use Discontinuat ion Side effects	Ongoing
----------------------	-------	---	--	----------------------	-------	--	---------

Additionally, we have adapted Mobile WACh for 3 pilot projects: Mobile WACh NEO (Saving Lives at Birth, PI: [name]), Mobile WACh PrIYA (Pre-exposure prophylaxis implementation in young women and adolescents) (sub-aim) (DREAMS, PI: [name]), and DAWN, a project for peripartum depression (sub-aim) (NIMH, PI: [name]) (66). In each instance we have accrued extensive experience adapting the platform for use among vulnerable populations and handling sensitive information such as SMS related to HIV management (59), depression (66) and adverse outcomes such as infant death (65).

Preliminary studies: mHealth and neonatal health

[figure not shown]

Figure 8: Components of the Mobile WACh NEO pilot

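### Protocol 12.4 promises without qualification that no sensitive information is texted, but the planned infant loss track sends messages of a kind the protocol elsewhere calls sensitive, and shared phones are eligible

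*Protocol*

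**What the plan says.** Protocol 12.4, under SMS, recognises that personal information could be disclosed to "others in situations where phones are shared or stolen". It answers at once: "However, we will not send any sensitive information via text". No exception is stated and sensitive is not defined.

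The same risk has other safeguards:

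- Section 12.3: "We will minimize these risks through counseling in the informed consent process and ensuring women understand the type of messaging that will occur".
- Section 12.4: "Study staff will specifically demonstrate example messages, to ensure potential cohort study participants agree to receipt of this information". Women enrol only if they find the messaging acceptable, and those in the intervention arm may stop the texts at any time.
- SAP 5.5: social harms, with violence and breach of confidentiality as examples, are monitored and go to the data monitoring board.

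On content, Protocol 11.6.i says: "Women who experience pregnancy or infant loss will be enrolled into an infant loss track where they will receive messages of support". The caption to Figure 10 repeats this. Section 7, summarising pilots on the same platform (the Mobile WACh NEO pilot among them), claims experience in "handling sensitive information such as SMS related to HIV management (59), depression (66) and adverse outcomes such as infant death (65".

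On who can see the phone, Table 2 in section 11.3 accepts "Daily access to a mobile phone (own or shared) on the Safaricom network" and women "Able to read and respond to text messages in English, Kiswahili or Luo, or have someone in the household who can help". The text below it limits assisted reading to a partner or relative with whom the woman is comfortable.

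**The concern.** A safeguard described in the ethics section should match the intervention described in the methods. Section 12.4 tells an ethics committee that the content of the texts protects women whose phones are seen by others. Section 11.6.i then builds in a set of texts whose recipients are, by definition, women who have lost a pregnancy or a baby. A message from that track can show a second reader that a loss has occurred, depending on its wording.

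The issue is participant protection, not the statistics. Endpoints, alpha, power and analysis are unaffected. The women most concerned are bereaved women who share a phone or have messages read to them. The SAP already treats breach of confidentiality and violence as harms worth tracking, so the sponsor regards disclosure as a real risk. If the protocol describes one of its protections wrongly, that risk cannot be weighed correctly.

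**Working it through.** **Comparison of the passages**

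1. *The promise.* Section 12.4 concerns what the study sends. It is absolute and is offered in answer to the shared or stolen phone risk.
2. *What the study sends.* Section 11.6.i makes loss-track texts a planned, outgoing part of the intervention, for pregnancy loss and for infant loss.
3. *Whether this is sensitive by the protocol's own usage.* Section 7 names infant death and depression as examples. Infant loss therefore matches directly. Pregnancy loss is not named and comes in only by inference, as another adverse outcome. The section 7 sentence describes earlier projects, but on the same platform and including the pilot of this intervention.
4. *Whether others may see it.* Section 11.3 admits shared phones and assisted reading.
5. *Result.* Statements 1 and 2 conflict under the usage in 3, and 4 makes the conflict matter.

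Dialogue about mood is a weaker case. Section 7 describes emotional support and psychoeducation as one of the intervention's mechanisms and reports that the pilot received texts about depressive symptoms. Those were texts from women. The documents do not show that routine messages or nurse replies carry sensitive content, so it can be said only that dialogue may touch on it.

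**Scale**

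The plan gives no figure for the loss track, so there is none to reproduce. The inputs are the SMS-arm size of 2,510 (Protocol sections 5 and 11.4) and the mortality values in Protocol Table 3, which run from 10.0 to 25.0 per 1000 across the control and intervention columns. One live birth per woman is assumed.

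Women eligible through neonatal death = 2,510 × rate / 1000:

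| Rate per 1000 | Source in Table 3 | Women |
|---|---|---|
| 10.0 | lowest intervention value | 25.1, about 25 |
| 12.2 | intervention value paired with 23.0 | 30.6, about 31 |
| 13.8 | highest intervention value | 34.6, about 35 |
| 23.0 | middle control value (no effect) | 57.7, about 58 |
| 25.0 | highest control value (no effect) | 62.8, about 63 |

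The range is about 25 to 63. Two things move it:

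- Pregnancy losses add to it; the documents give no rate.
- Section 11.5.ii anticipates that half of women who lose a baby will want to stay connected. Half of 25.1 to 62.8 is about 13 to 31 with continuing contact after a neonatal death.

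The proportion sharing a phone is not given, so no count of exposed women can be derived. Each 10 percentage points of sharing corresponds to 2.5 to 6.3 of the 25 to 63 eligible women (25.1 × 0.10 and 62.8 × 0.10).

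**The case against.** The strongest reply is that one loosely worded sentence is being read as if it were the whole safeguard. A reader might infer that women on shared phones have no protection. The documents do not support that: counselling, example messages, the acceptability condition, SMS withdrawal and monitoring of social harms do not depend on the sentence. Assisted reading is limited to a person the woman is comfortable with, and section 11.3 says the approach was developed with mothers in Kenya and has been used successfully.

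A reader might also infer that women consent on a false description, or that the counselling rests on the promise. Neither can be shown. The consent forms and message texts are not available, and section 12.3 ties counselling to the type of messaging rather than to an assurance that nothing sensitive is sent. How much a loss message reveals is likewise unknown.

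Three further points are fair. Section 7 does not name pregnancy loss. What women choose to text is not what the study sends. Control-arm mortality alone would overstate the number of women in the SMS arm if the intervention works, which is why the range above starts at the lowest intervention value.

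These points narrow the issue without removing it. The sentence is unqualified, the loss track is planned, and section 7 treats texts about infant death as sensitive. Counselling and example messages close the gap only if they cover loss messages, and the protocol does not say that they do. Withdrawal helps a bereaved woman only if she acts before a message arrives; otherwise it may already have been seen.

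**Conclusion.** The contradiction holds for the loss track. The promise in section 12.4 is not consistent with section 11.6.i under the protocol's own use of the word sensitive: directly for infant death, by inference for pregnancy loss. It is a correctable misstatement of one protection among several. It does not show that protection is absent or that women are misinformed.

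About 25 to 63 SMS-arm women would be eligible for the loss track through neonatal death, before pregnancy losses are added, with about half of bereaved women expected to want continued contact. This rests on the Table 3 rates and one live birth per woman. How many of them share a phone or rely on a reader cannot be stated from the documents. The numbers are small, but the group is vulnerable and the correction is cheap, so it should be made.

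**What to change.** 1. Reconcile sections 12.4 and 11.6.i by removing the sentence or qualifying it. Defining sensitive, or excepting the loss track explicitly, would also serve.
2. State in 12.3 and 12.4, and in the consent form if it is not already there, that messages may reveal a pregnancy or infant loss and that dialogue may touch on mood or infant illness.
3. At consent, record whether a woman with a shared or assisted phone accepts loss-related messages on it. SAP Table 5.1 already lists phone sharing and unassisted reading as baseline variables, so the women concerned can be identified.

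Showing a loss message to every pregnant woman at enrolment is debatable and is not needed for this correction.

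The cost is a wording amendment and one consent item, and a few women may decline some message types. Sample size, alpha and analysis do not change.
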